### **3. STUDY OBJECTIVES AND ENDPOINTS**

Descriptive assessments of long-term efficacy and safety will be made between the parent study Baseline and Week 52, and between the parent study Baseline the end of the extension study (Week 104) for the following parent study treatment groups:

- Parent Study Group A: Randomized to 24 weeks of oral relugolix 40 mg once daily co-administered with 1.0 mg estradiol and 0.5 mg norethindrone acetate in the parent study;
- Parent Study Group B: Randomized to 12 weeks of oral relugolix 40 mg once daily followed by 12 weeks of oral relugolix 40 mg once daily co-administered with 1.0 mg estradiol and 0.5 mg norethindrone acetate in the parent study;
- Parent Study Group C: Randomized to placebo in the parent study.

The parent study Baseline will be used as the reference point for this extension study for all change from baseline-related endpoints. The pain scores during the Baseline Pain Assessment Period of the parent study will establish the patient's baseline for both the parent study and the extension study.

In women with endometriosis-associated pain, the study objectives and corresponding endpoints are as follows:

Objectives	Endpoints
Primary Efficacy	

To be assessed at Week 52
 
 
To evaluate long-term efficacy of relugolix 40 mg once daily co-administered with low-dose estradiol and norethindrone acetate for up to 52 weeks, among patients who previously completed a 24-week treatment period in one of the parent studies (MVT-601-3101 or MVT-601-3102), on endometriosis-associated pain.
 
 
To be assessed at Week 104
 
 
To evaluate long-term efficacy of relugolix 40 mg once daily co-administered with low-dose estradiol and norethindrone acetate for up to 104 weeks, among patients who previously completed a 24-week treatment period in one of the parent studies (MVT-601-3101 or MVT-601-3102), on endometriosis-associated pain.
 
	
To be assessed at Week 52
 
 
Proportion of women who respond or maintain response at Week 52/Early Termination, based on their dysmenorrhea Numerical Rating Scale (NRS) scores;
 
Proportion of women who respond or maintain response at Week 52/Early Termination, based on their NMPP NRS scores.
 
 
To be assessed at Week 104
 
 
Proportion of women who respond or maintain response at Week 104/Early Termination, based on their dysmenorrhea NRS scores;
 
Proportion of women who respond or maintain response at Week 104/Early Termination, based on their NMPP NRS scores.
 

Secondary Efficacy	

To be assessed at Week 52 and Week 104
 
To evaluate long-term efficacy of relugolix 40 mg once daily co-administered with low-dose estradiol and norethindrone acetate, among patients who previously completed a 24-week treatment period in one of the parent studies (MVT-601-3101 or MVT-601-3102), on the following:
 
 
Function, as measured by the Endometriosis Health Profile (EHP)-30 Pain Domain;
 
Dysmenorrhea, as measured by the NRS for dysmenorrhea;
 
Patient Global Impression of Change (PGIC) for dysmenorrhea;
 
NMPP, as measured by the NRS for NMPP;
 
Overall pelvic pain, as measured by the NRS;
 
	
To be assessed at Week 52 and Week 104, unless otherwise specified
 
 
Change from the parent study Baseline in the EHP-30 Pain Domain scores;
 
Change from the parent study Baseline in the mean dysmenorrhea NRS score;
 
Proportion of patients who are better or much better on the PGIC for dysmenorrhea (at Week 52 only);
 
Change from the parent study Baseline in the mean NMPP NRS score;
 
Change from the parent Baseline in the mean NRS score;
 

Objectives	Endpoints

 
• Analgesic use;
 
• PGIC for NMPP;
 
• Dyspareunia, as measured by the NRS;
 
• PGIC for dyspareunia;
 
• Dyspareunia-related functional effects (Subject Modified Biberoglu and Behrman [sB&B]);
 
• To determine the benefit of relugolix 40 mg once daily co-administered with 24 weeks of low-dose estradiol and norethindrone acetate compared with placebo on function measured by the EHP-30 Pain Domain;
 
• Patient Global Assessment (PGA) for pain;
 
• PGA for function;
 
• Endometriosis-associated quality of life, as measured by the EHP-30 Control and Powerlessness, Social Support, Emotional Well-Being, and Self-Image domains;
 
• Dysmenorrhea-related functional effects (sB&B);
 
• NMPP-related functional effects (sB&B).
 
	
 
• Proportion of patients not using opioids;
 
• Proportion of patients not using analgesics;
 
• Proportion of patients who are better or much better on the PGIC for NMPP (at Week 52 only);
 
• Change from the parent study Baseline in the mean dyspareunia NRS scores;
 
• Proportion of patients who are better or much better on the PGIC for dyspareunia (at Week 52 only);
 
• Change from the parent study Baseline in the mean dyspareunia functional impairment on the sB&B scale;
 
• Proportion of responders based on EHP-30 Pain Domain scores;
 
• Change from the parent study Baseline in severity scores on the PGA for pain;
 
• Change from the parent study Baseline in function impairment on the PGA for function;
 
• Change from the parent study in each of the non-pain EHP-30 domains (Control and Powerlessness, Social Support, Emotional Well-Being, and Self-Image);
 
• Change from the parent study Baseline pain assessment period in dysmenorrhea-related functional effects (sB&B);
 
• Change from the parent study Baseline pain assessment period in NMPP-related functional effects (sB&B).
 

Safety	

To evaluate the safety of relugolix 40 mg once daily co-administered with low-dose estradiol and norethindrone acetate for up to 104 weeks, among patients who previously completed a 24-week treatment period in one of the parent studies (MVT-601-3101 or MVT-601-3102), including:
 
 
• Adverse events;
 
	
To be assessed at Week 52 and Week 104
 
 
• Incidence of adverse events;
 

Objectives	Endpoints

 
Changes in bone mineral density.
 
	
 
Percent change from the parent study Baseline in bone mineral density at the lumbar spine (L1-L4), femoral neck, and total hip as assessed by dual-energy x-ray absorptiometry (DXA).
 

Pharmacodynamic	

 
To evaluate the pharmacodynamic effects of relugolix 40 mg once daily co-administered with low-dose estradiol and norethindrone acetate for up to 104 weeks, among patients who previously completed a 24-week treatment period in one of the parent studies (MVT-601-3101 or MVT-601-3102), on estradiol.
 
	
To be assessed at Week 52 and Week 104
 
 
Change from parent study Baseline in predose concentrations of serum estradiol.
 

Exploratory	

 
To evaluate the benefit of relugolix 40 mg once daily co-administered with low-dose estradiol and norethindrone acetate on endometriosis-associated quality of life (EHP-30 total score), work (EHP Work Domain), and patient-reported quality of life outcomes (European Quality of Life Five-Dimension Five-Level Scale [EQ-5D-5L]) for up to 104 weeks among patients who previously completed a 24-week treatment period in one of the parent studies (MVT-601-3101 or MVT-601-3102).
 
	
To be assessed at Week 52 and Week 104
 
 
Change from Baseline in the EHP-30 scale total score;
 
Change from Baseline in the EHP Work Domain score;
 
Change from parent study Baseline in the EQ-5D-5L.
 

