--	---

Duration of Treatment	
Study treatment will be self-administered for 80 weeks (Open-Label Treatment Period).
 
Concomitant Medicinal Products Systematically Prescribed for All Study Patients
 
Two protocol-specified analgesics include a first-line non-steroidal anti-inflammatory drug and a second-line opioid or opioid/acetaminophen or opioid/paracetamol combination for endometriosis-related pain relief as required. The specific analgesic drugs offered may differ for different countries or regions. The analgesics for each patient will be the same as those prescribed for her during the parent study.

Criteria for Evaluation	
Descriptive assessments of long-term efficacy and safety will be made between the parent study Baseline and Week 52, and between the parent study Baseline and the end of the extension study (Week 104) for the following parent study treatment groups:
 
 
• Parent Study Group A: Randomized to 24 weeks of oral relugolix 40 mg once daily co-administered with 1.0 mg estradiol and 0.5 mg norethindrone acetate in the parent study;
 
• Parent Study Group B: Randomized to 12 weeks of oral relugolix 40 mg once daily followed by 12 weeks of oral relugolix 40 mg once daily co-administered with 1.0 mg estradiol and 0.5 mg norethindrone acetate in the parent study;
 
• Parent Study Group C: Randomized to placebo in the parent study.
 
 
The parent study Baseline will be used as the reference point for this extension study for all change from baseline-related endpoints. The pain scores during the Baseline Pain Assessment Period of the parent study will establish the patient's baseline for both the parent study and the extension study.
 
Primary Efficacy Endpoints
 
Week 52
 
 
• Proportion of women who respond or maintain response at Week 52/Early Termination, based on their dysmenorrhea NRS scores;
 
• Proportion of women who respond or maintain response at Week 52/Early Termination, based on their NMPP NRS scores.
 
 
Week 104
 
 
• Proportion of women who respond or maintain response at Week 104/Early Termination, based on their dysmenorrhea NRS scores;
 
• Proportion of women who respond or maintain response at Week 104/Early Termination, based on their NMPP NRS scores.
 

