#### **4.5. Removal of Patients from Therapy**

Completion of the Week 104 visit defines completion of the study. Patients may withdraw consent to participate in the study and discontinue treatment at any time for any reason. Investigators or the medical monitor may remove patients from therapy under this protocol for reasons of safety and/or lack of compliance as discussed below. Patients removed from therapy for any reason will undergo the assessments for the Early Termination visit (see the Week 104 visit on the Schedule of Activities, Section 1.1) and will have a Follow-up visit to assess safety approximately 30 days after the end of study drug treatment (ie, after the patient's last dose of study medication). When patients complete the study or early terminate from the study, they must be deactivated from the study in the interactive voice response system/interactive web response system (IVRS/IWRS), eDiary, and tablet device.

The following safety and/or compliance events will result in the removal of patients from therapy either permanently or until the etiology of the problem has been identified and resolved:

- Any adverse event that is intolerable to the patient and that cannot be ameliorated by the use of adequate medical intervention, or that in the opinion of the investigator or medical monitor would lead to undue risk to the patient if dosing continued;
- If it is discovered after enrollment that a patient failed to meet protocol entry criteria and continued participation poses an unacceptable risk to the patient's health;
- If the following liver test abnormalities develop, study drug should be discontinued immediately with appropriate clinical follow-up (including repeat laboratory tests, until a patient's laboratory profile has returned to normal/baseline status):
  - ALT or AST > 8 x ULN; or
  - ALT or AST > 5 x ULN and persists for more than 2 weeks; or
  - ALT or AST > 3 x ULN in conjunction with elevated total bilirubin > 2 x ULN or international normalized ratio (INR) > 1.5; or
  - ALT or AST > 3 x ULN with appearance of fatigue, nausea, vomiting, right upper quadrant pain or tenderness, fever, rash and/or eosinophilia (> 5%);

- 
- QT interval by the Fridericia correction (QTcF) prolongation of more than 500 msec read by a cardiologist;
  - Evidence of endometrial hyperplasia or endometrial carcinoma on endometrial biopsy;

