### **6.3. Early Termination Visit and Follow-Up Visit**

All patients withdrawing from the study prior to Week 104 will complete an Early Termination visit. The Early Termination visit procedures are identical to those of Week 104. An endometrial biopsy is required for all patients at the Early Termination visit except for patients whose last dose of study drug was taken during Week 32 or earlier or within four weeks after completion of the Week 52 endometrial biopsy. However, the endometrial biopsy may be obtained if it will aid in the evaluation of an ongoing adverse event. Follow-up bone densitometry findings for patients who terminate from the study early will proceed according to the rules provided in Section 6.5.2.6.

Patients (including those who complete the Week 104 visit and those who withdraw early from this study) will have a Follow-Up visit approximately 30 days after the last dose of study drug, or prior to the date of initiation of another investigational agent or hormonal therapy affecting the hypothalamic-pituitary-gonadal axis or surgical intervention or other invasive procedure for endometriosis, whichever occurs first. However, for patients who enroll directly into another relugolix clinical study upon completion of the Week 104 visit, the Follow-Up visit may be waived.

The Follow-Up visit will be used to assess safety after discontinuation of study treatment including adverse events, clinical safety laboratories, and return of menstruation. Refer to the Schedule of Activities (see Section 1.1) for individual study visit procedures during the Follow-Up visit.

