### **9.4. Efficacy Analyses**

Unless otherwise specified, efficacy analyses will be conducted using the Extension Study Population.

Efficacy endpoints will be summarized by the original treatment groups assigned in the parent study.

The point estimates and 2-sided 95% confidence intervals (CI) for the primary efficacy endpoints (proportion of responders based on dysmenorrhea NRS scores and use of rescue analgesic medications, proportion of responders based on NMPP scores and use of rescue analgesic medications) will be calculated.

A responder at a given time point and for a specific type of pain (dysmenorrhea or NMPP) is defined as a patient who had a reduction in that type of pain from Baseline in the parent study greater than or equal to a pre-determined threshold and who did not have an increase in the use of rescue analgesic medications for endometriosis-associated pain compared with the use at Baseline. Patients who had a pain reduction less than the pre-determined threshold or who had an increase in the use of analgesics for endometriosis-associated pain will be considered non-responders. The pain reduction thresholds will be determined for NMPP and dysmenorrhea separately (see the SAP for details) for the parent studies and these same thresholds will be applied to this study.

Baseline values are calculated using the Baseline pain assessment period, which is defined as the period from the date of the first dose of placebo in the parent study Run-In Period through the day prior to the first dose of randomized study drug. Patients' average NRS pain scores and use of rescue analgesic medications for endometriosis-associated pain (dysmenorrhea or NMPP) will be compared between a given visit-specific pain assessment period (eg, Week 28, Week 32, etc.) and the Baseline pain assessment period. The visit-specific pain assessment period is defined as the last 35 calendar days immediately prior to and including the last dose of study drug treatment received prior to the visit date.

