For endpoint of proportion of responders based on EHP-30 Pain Domain scores, a responder is defined using the same within-patient score change threshold determined from the parent studies.

Details on the endpoint analyses including derivations, handling of missing data, and statistical methods will be provided in the SAP.

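### The primary endpoints let an Early Termination assessment stand in for Week 52 or Week 104, so early stoppers with controlled pain can count as responding at a week they never reached on treatment

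*Protocol*

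**What the plan says.** Section 3 and the Synopsis (Criteria for Evaluation) define four primary efficacy endpoints, for dysmenorrhea and for NMPP at each of two time points. All four carry the Early Termination alternative, for example "Proportion of women who respond or maintain response at Week 104/Early Termination, based on their dysmenorrhea NRS scores" and "Proportion of women who respond or maintain response at Week 52/Early Termination, based on their NMPP NRS scores". The secondary efficacy endpoints in Section 3 are set at Week 52 and Week 104 without that alternative.

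Section 9.4 (Amendment 3.1) takes the pain window as the "last 35 calendar days immediately prior to and including the last dose of study drug treatment received prior to the visit date". A responder must reach the pain-reduction threshold and must not have increased rescue analgesic use. The stated routes to non-response are the reverse of these: "Patients who had a pain reduction less than the pre-determined threshold or who had an increase in the use of analgesics" for endometriosis-associated pain. Discontinuation is not among them.

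Section 6.3 gives every early stopper an assessment: "All patients withdrawing from the study prior to Week 104 will complete an Early Termination visit". Section 4.5 lists reasons for removal that need not involve pain, such as "Any adverse event that is intolerable to the patient and that cannot be ameliorated by the use of adequate medical intervention", bone loss, liver test abnormalities and pregnancy. Section 9.2 (Amendment 3.1) keeps every enrolled woman who took any extension drug in the efficacy population. Section 9.4 ends by deferring detail: "Details on the endpoint analyses including derivations, handling of missing data, and statistical methods will be provided in the SAP".

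**The concern.** The primary objective is efficacy over as long as 104 weeks, and the Week 104 proportion will be read as evidence that relief lasts two years. As defined, it mixes two quantities: response at Week 104 among women who got there, and response at the last on-treatment window among women who did not. A woman who leaves after the Week 36 scan because of bone loss, with her pain well controlled, can be scored as maintaining response at Week 104.

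The study has one arm and Section 9 plans no formal treatment comparisons, so the proportion is read at face value. Nothing in the endpoint as worded shows how much of it comes from women who had already stopped.

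**Working it through.** **The plan's own figure.** The only sample-size figure is about 800 women, given as 67% of 1200 (Section 9.3). 800/1200 = 66.7% and 0.67 × 1200 = 804, so it reproduces. It is used here only to turn percentages into women. The protocol states no dropout rate and no expected response rate.

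**Notation (all three values are assumptions).** d = share of the Extension Study Population stopping before the scheduled week; rC = response rate among those who reach it; rE = response rate at Early Termination among stoppers. Every woman is taken to have an evaluable window.

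**Formulas.**
- As worded: (1 − d) × rC + d × rE
- Stopping counted as non-response: (1 − d) × rC
- Difference: d × rE
- As worded minus completers only: d × (rE − rC), which is zero or negative whenever rE ≤ rC

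**Difference d × rE, in percentage points.**

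| d | rE = 0% | rE = 30% | rE = 50% | rE = 75% |
|---|---|---|---|---|
| 10% | 0 | 3.0 | 5.0 | 7.5 |
| 20% | 0 | 6.0 | 10.0 | 15.0 |
| 30% | 0 | 9.0 | 15.0 | 22.5 |
| 40% | 0 | 12.0 | 20.0 | 30.0 |

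**One case in full.** Take d = 20%, rC = 75%, rE = 50%.
- As worded: 0.80 × 0.75 + 0.20 × 0.50 = 0.60 + 0.10 = 70%.
- Stopping as non-response: 0.80 × 0.75 = 60%. The gap is 10 points, or 80 of 800 women.
- Completers only: 75%, so the figure as worded is 5 points lower than this.

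**Against sampling error.** The Wald 95% half-width is 1.96 × √[p(1 − p)/n]. At p = 70% it is 3.2 points for n = 800, and 5.5 points for a parent-study group of about 267 (equal thirds assumed). Over d = 10–40%, rE = 30–75% and rC = 75% or 85%, it runs from about 2.5 to 3.4 points at n = 800 and from about 4.4 to 5.9 points at n = 267. In every calculated case with d of 20% or more and rE of 30% or more, the choice of definition moves the result by more than the half-width, even for a single parent-study group.

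**The case against.** The strongest reply is that the endpoint is openly labelled, and that efficacy over a period of up to 104 weeks can fairly be summarised by the last on-treatment assessment. Which estimand should lead is a choice on which statisticians differ. No success criterion is attached to these endpoints, so the wording cannot cause a false claim of success. This stands, and it is why the point does not call for replacing the primary endpoint.

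Three stronger readings are tempting, and the documents do not support them.
- *That all early stoppers are counted as responders.* They are not. Each must reach the pain threshold without increased analgesic use, so a woman who leaves because her pain returned would usually be a non-responder.
- *That the reported proportion is overstated whatever the comparison.* It is higher only than under a rule where stopping is failure. In the case above it is below the completers' rate.
- *That the size of the effect is known.* The protocol supplies none of d, rC or rE.

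It may also be said that the SAP, which is not shown, will settle the matter. It may settle windows with too few diary entries. After Week 52 the diary runs only in Weeks 57–65, 71–78, 85–91 and 98–104, so a stop near Week 57 or Week 84 has essentially no diary data in its 35-day window. But putting Early Termination in place of the scheduled week is part of the protocol's own endpoint definition. The point rests on that definition and does not complain of a missing SAP rule.

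Finally, counting every stopper as a failure is itself a conservative convention. It scores exits for pregnancy (Section 4.5) or interrupted drug supply (Appendix 9) as non-response. This also stands, and is met by showing the reasons for stopping.

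**Conclusion.** The point holds in a limited form. All four primary endpoints allow the Early Termination assessment to stand in for Week 52 or Week 104, and no stated rule makes discontinuation a non-response. Women who stop early with controlled pain and no increase in analgesic use can therefore be counted as maintaining response at a week they did not reach on treatment.

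Relative to counting stopping as failure, the excess is d × rE: 3 to 30 percentage points under assumed ranges of 10–40% stopping and 30–75% of stoppers responding, and zero if none respond at exit. The ranges are illustrative and not taken from the protocol. The endpoint is a legitimate on-treatment summary, but on its own it does not show durability at Week 52 or Week 104.

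**What to change.** For each primary endpoint:
- Report alongside it the proportion of the Extension Study Population still on treatment and meeting the responder definition in the scheduled Week 52 (Week 104) window, with early terminators as non-responders.
- Label the version that includes Early Termination as *response at last on-treatment assessment*.
- Show how many of its responders come from an Early Termination assessment, by reason for stopping.
- Base any statement about durability at Week 52 or Week 104 on the scheduled-week figure.

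The cost is wording, one more row per table and the breakdown by reason. The data are already collected, and the last diary cycle, Weeks 98 to 104, is long enough to hold the 35-day window. The downside is a second figure that will be equal or lower, under a conservative rule that also counts non-efficacy exits as non-response. The breakdown by reason lets the reader see how many of the Early Termination responders left for such reasons.
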